1.3 Design

The proposed design is a pragmatic two-arm trial. Children randomised to the intervention group will start Otovent treatment immediately, whilst treatment in the control group will be delayed until the end of a 3 month comparison period. Children in both trial groups will undergo tympanometry at baseline, 1 and 3 months but usual clinical care will not be otherwise constrained. In the intervention group, children with normal tympanometry in both ears at 1 month will discontinue autoinflation whilst those with persisting OME will be encouraged to continue for up to two further months.

The intervention will be offered to control children with residual tympanic dysfunction at the end of the 3 month comparison period as we believe it will substantially increase recruitment to the study. The main study period up to 3 months will evaluate the additional benefit over usual care of a standardised purpose manufactured autoinflation device (Otovent) in improving OME, in school aged children in primary care, as assessed by a more objective method (tympanometric resolution) than history, at both1 and 3 months.

We will assess cost effectiveness at the end of the randomised 3 month active monitoring period as the health economic main outcome in terms of costs and QALYs, and will also include resolution of OME in the shorter term (1 month), and use an extrapolated scenario analysis including the data from the 6 month audit for longer term projections of costs.

A period of three months active monitoring (watchful waiting) has been chosen as it is best current practice. Good clinical practice also requires that children deemed as severe or protracted at the outset may need to be referred for surgery immediately and excluded from the trial; it is envisaged that this group will be very small.

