Children randomised to receive autoinflation will be shown by the research nurse how to perform autoinflation. The guardian will also be involved to demonstrate use of the balloon for the child to copy, to improve compliance. When the balloon has thus been stretched sufficiently through use, the child will be encouraged to blow up the balloon for themselves, firstly through the mouth, then by blowing out through their nose. Recipients will be provided with the nasal fitting device, with 5 balloons per trial intervention pack, containing pictorial and written instructions on correct use. Additional website and You-Tube address details will be supplied so that children and parents can watch a video of the method whenever they choose, to provide support on correct performance of the technique. Micro-tympanometry will also be done immediately after per-nasal inflation of the balloon to record the tympanogram type, either A, C1, C2, or B (a sequence of increasing severity). This is being done to see if any immediate conversion of tympanogram type to one of improved middle ear pressure predicts results at 1 month. Parents will be phoned at home by the nurse after 2-4 days, primarily as a supportive measure with the nurse providing any additional requested information for parents and children that should also encourage compliance. The nurse will take note of any untoward effects and discuss any queries or issues. Where compliance is reported as unsatisfactory a second nurse appointment will be offered, when the child and guardian can be given further specific pragmatic tips and education about improving the technique based directly on observation of use. ([name] has provided useful practical advice on procedures which we have implemented in the pilot). After 1 month those not cured using tympanometric criteria in the intervention arm will be encouraged to use a further 2 months course of balloons for autoinflation, supplied in 2 boxes.

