3.3 Justification of an open pragmatic trial

Because of the nature of the procedure use of a placebo and blinding are not possible. However effectiveness outcomes for the NHS are best measured by such a method, and will reflect real life outcomes. The use of an objective primary outcome - tympanometric cure, one that is also independently verifiable, will reduce potential subjective biases in the study. We will use faxes of tympanograms to the main co-ordinating centre to improve validity of this outcome and check correct categorisation of baseline, one and three month recordings. We will estimate placebo effects of using the device by asking how effective parents and children believed the device to be at 2-4 days.

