5. RISKS AND ANTICIPATED BENEFITS

As with all trials there is always a degree of risk to participants, however in this particular trial the risks are estimated to be extremely small. No side effects have been reported from current trials. The main theoretical side effect is an increase in upper respiratory infection due to air pressures generated in the nasal cavity equivalent to being submerged under 2-3 foot of water somehow spreading infected mucus up the Eustachian tubes. No such increase in infection rate has been noted in the trials so far and in fact the incidence of respiratory tract infection was observed to be higher in the control group in the only previous British study.²³

The fact that fluid behind the ear on tympanometry is found less commonly in treated groups in most trials to date also means that ear infections are likely to be less when using the device. The ICH-GCP guidelines for definitions of adverse events/reactions will be followed, and all adverse events/reactions will be recorded. The co-ordinating centre's standard operating procedure for safety reporting in studies not involving an investigational medicinal product will be fully complied with, including reporting of all serious adverse events (e.g. any unplanned hospitalisation) to the sponsor immediately, and as will all related unexpected serious adverse events. In addition to any expedited reports, annual safety reports will be submitted to the main REC.

Placebo treatment is not planned at all in this children's study. All children/guardian participants will be offered the intervention after 3 months of the study if they were not initially randomised to the +autoinflation arm, and the fluid/effusion has not gone away by that time.

Using the combinations of:"natural cure+ standard care +/- any treatment effect from adjunctive use of the device," constitutes possibly the best primary care approach currently available to evaluate. On the basis of the NICE 2009 guideline which recommends active monitoring for OME for 3 months, and states "autoinflation may be beneficial in older children". Although standard care will be fully detailed in the study there is no evidence for any significant effect of any of the commonly used treatments on tympanometric resolution. The level of trial care and aftercare will be thorough and, as proposed, will meet high standards.

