7. OUTCOME MEASURES

7.1 Main outcome

The primary outcome will be a tympanometric measure. Tympanometric resolution in ears will be defined as conversion of the B-type highly predictive of effusion to either an A or C1 type i.e. back to normal pressures. Type C2 will not be considered sufficiently cured or resolved because the PPV for effusion of C2 remains modest at 55%.³⁴

The difference in proportions of children showing resolution to A or C1 in at least one B (affected) ear per child at one month is the main study outcome.

This outcome is chosen based on evidence from the Cochrane review and hence is the basis for the sample size calculation. It is also a robust outcome and less likely to be affected by any placebo effect of intervention. Otoscopy will be performed by the trained nurse prior to tympanometry to improve method validity. Nurses will attend a day course that includes full relevant instruction in practical tympanometry procedures and will use a learning-set of tympanogram print outs to categorise type before collecting data as a training aid. The MTP-10 micro-tympanometers used (sufficient stock is available from the recent GNOME trial) are being serially re-calibrated for the proposed new trial and all have a print out facility. A central trial fax-hotline will be used for tympanogram interpretation in the study for "at-point-of-care" support, and will be the basis for continuing training of operators to improve repeatability and validity of the method. (Tympanometric skills will be assessed in initial samples of consecutive cases per nurse-operator).

Difference in tympanometric baseline severity is likely to be an effect modifier and will be accounted for in both the minimisation protocol and secondary analysis (see relevant sections).

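### Belief in the device at 2-4 days measures perceived effectiveness; it cannot estimate a placebo effect as section 3.3 claims

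*Protocol*

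**What the plan says.** Section 3.3 of the protocol justifies the open design. It begins by accepting that "Because of the nature of the procedure use of a placebo and blinding are not possible", and section 5 confirms that "Placebo treatment is not planned at all in this children's study". Section 3.3 then relies on the pragmatic aim, on an objective primary outcome, and on tympanograms faxed to the co-ordinating centre so that their categorisation can be checked. It ends with this commitment: "We will estimate placebo effects of using the device by asking how effective parents and children believed the device to be at 2-4 days".

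Three other places bear on what that question can measure:

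- Section 1.3 says that "treatment in the control group will be delayed until the end of a 3 month comparison period".
- Section 3.2.3, in its paragraph on children randomised to autoinflation, describes the only contact at that time: "Parents will be phoned at home by the nurse after 2-4 days, primarily as a supportive measure". It does not mention a belief question.
- The same paragraph says that "Micro-tympanometry will also be done immediately after per-nasal inflation of the balloon to record the tympanogram type", and gives the reason: "This is being done to see if any immediate conversion of tympanogram type to one of improved middle ear pressure predicts results at 1 month".

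Section 8.2 gives the belief item no place in the analysis. Section 7.1 says of the primary outcome: "It is also a robust outcome and less likely to be affected by any placebo effect of intervention".

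**The concern.** A placebo effect is a contrast: the outcome with expectation against the outcome without it, with the active treatment held the same. Section 3.3 proposes to obtain it from a single rating given after some days of use. A family whose child is already improving will tend to rate the device highly, and that child is also more likely to be clear at 1 month. Belief would then predict outcome even if the placebo effect were nil.

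What is at stake is how the secondary results are read. The symptom diaries, the OMQ-14 and the proxy Health Utilities Index are completed by parents who know the allocation, and the last of these feeds the cost-per-QALY analysis (section 8.3). Expectation is a leading source of bias for these measures. A figure labelled as the placebo effect would give readers false assurance about that bias.

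**Working it through.** The plan gives no number for this point, so there is no figure to reproduce. The check is whether the planned data could identify the quantity claimed.

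**Step 1: what the contrast needs, against what the protocol provides.**

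- *A comparator given expectation without active treatment.* None: sections 3.3 and 5 rule out placebo.
- *A control-arm rating of use.* Not available: under section 1.3 controls have no device to rate until after 3 months.
- *Expectation measured before treatment can act.* The rating in section 3.3 comes at 2-4 days, after use has begun.
- *No real effect by the time of the question.* Section 3.2.3 treats immediate conversion of the tympanogram as possible and measures it. Real response may therefore already have shaped belief.
- *A neutral setting for the question.* The only contact described at 2-4 days is a call meant to support the family and encourage compliance.

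**Step 2: illustration that the data cannot separate the explanations.** The 1-month cure outcome is used only because the protocol gives rates for it. The same logic applies to the parent-reported outcomes.

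Inputs from section 8.1: control cure 45%, odds ratio 2.4.

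- Device-arm odds = (0.45/0.55) × 2.4 = 1.964
- Device-arm cure = 1.964/2.964 = 0.6626

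Assumed, not in the protocol: 70% of children later cured come from families who believed in the device at 2-4 days, and 45% of the others.

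Joint proportions in the device arm:

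- Believed and cured: 0.6626 × 0.70 = 0.4638
- Did not believe, cured: 0.6626 × 0.30 = 0.1988
- Believed, not cured: 0.3374 × 0.45 = 0.1518
- Did not believe, not cured: 0.3374 × 0.55 = 0.1856

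What the trial would observe:

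- Believers: 0.4638 + 0.1518 = 61.6%
- Cure in believers: 0.4638/0.6156 = 75.3%
- Cure in non-believers: 0.1988/0.3844 = 51.7%
- Difference: 23.6 points

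Two opposite explanations produce exactly this table:

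- **A: no placebo effect.** Belief merely follows early improvement or good prognosis. The contribution of belief to cure is 0.
- **B: belief causes the whole difference.** Belief is unrelated to prognosis and raises cure from 51.7% to 75.3%. Its contribution to the arm's cure rate is 0.616 × 23.6 = 14.5 points.

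The randomised comparison does not settle the matter. The overall difference is 66.3 − 45 = 21.3 points under both. Under A none of it comes from belief; under B, counting controls as having no belief effect, 14.5 points do and 51.7 − 45 = 6.7 do not. A simulation of 2,000,000 device-arm children under each explanation gave the same belief rate, the same two cure rates and the same 23.6-point difference.

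The 14.5 depends on the assumed 70% and 45%. The failure to identify does not: any association between belief and outcome can be produced either way.

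**The case against.** The strongest reply is that this is one loosely worded sentence at the edge of the plan. Section 3.3 does not rest its case on it: the objective, independently checked tympanogram comes first. No analysis in section 8.2 uses the item. This stands, and it limits the point to a matter of wording and interpretation.

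Three stronger readings are tempting, and the documents do not support them.

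- *That only device users are asked.* A reader might infer this from the reference to using the device, from where section 3.2.3 places the call, and from the delayed treatment of controls. It is a strong inference, but the protocol does not say it outright. The conclusion does not depend on it, since controls would have no use to rate.
- *That expectation is never measured before treatment.* Section 3.2.3 gives parents in both arms a short study-specific questionnaire at entry whose items are not shown. The absence of an expectation item is not established.
- *That the figure will be subtracted from the treatment effect.* Nothing in the protocol says so.

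It is also fair to say that the protocol does not state that parents are told the result of the tympanogram taken after inflation. The argument does not need this, because a child may notice real improvement without being told.

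Leaving the handling of the item to an analysis plan would not rescue the claim. The limitation lies in the design and in when the question is put, and analysis of that answer cannot supply the missing contrast.

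**Conclusion.** The point holds as a fault in what section 3.3 claims. The 2-4 day answer describes perceived effectiveness among families who have begun treatment. It cannot be separated from early real response, ease of use, compliance and nurse support, and so cannot estimate a placebo effect.

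The consequence is small. The planned primary comparison, its sample size and its test are unchanged. What matters is the interpretation of the parent-reported outcomes, where the size of any expectation bias cannot be bounded from the plan. The range of 0 to about 14.5 points rests on invented belief rates; it shows only that the data cannot tell the explanations apart and does not predict this trial's results.

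The conclusion rests on three features the protocol does state: no placebo, no device treatment for controls before 3 months, and a question put after treatment has started.

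**What to change.** Replace the last sentence of section 3.3. Say that parents' and children's view of the device at 2-4 days will be reported as a description of perceived effectiveness and acceptability, and drop the claim to estimate placebo effects. Add that expectation bias in the parent-reported outcomes of this open trial (diaries, OMQ-14, Health Utilities Index) cannot be quantified.

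Optionally, if expectation is to be explored, ask one question of parents in both arms before randomisation and report its relation to outcome as an exploratory association only. It would not be a placebo-effect estimate either: baseline expectation is not randomised and may go with severity or later compliance, and section 8.2 already says that the trial is not powered for effect modification.

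The cost is a change of wording and, if the option is taken, one baseline item. The only downside is that the trial gives up a claim it cannot support.

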3.4 Intervention being assessed

The intervention has two elements: the prescribing of the device, and provision of brief training/support, with the latter designed explicitly to be generalisable to everyday general practice.

The use of the purpose manufactured device (Otovent) will be evaluated as supplied to the trial by Kestrel Medical Ltd. Poole, Dorset. One standard pack containing the nasal tip- a safe spherical connecting device made of plastic and 5 quality checked latex balloons. Packs will be provided to those randomised to the immediate autoinflation treatment group. One pack will cover 1 month of treatment due to decreasing elasticity of each balloon over about a weeks use. All children with a residual B tympanogram at 1 month will be offered 2 further standard packs to cover 2 further months of treatment. Uptake will be recorded for concordance/compliance considerations.

The child will be instructed to inflate the balloon once via each nostril in the morning, after school, and at bedtime (x6 total). A sticker book diary/wall chart will be provided for the children to encourage participation. All children will receive usual clinical care, and the intervention will be in addition to this. We intend to use practical delivery advice from other relevant trials^{22,23} e.g. use of parents to demonstrate the method, use of the extended Valsalva manoeuvre and or Politzer equivalent, with use of step-wise techniques for very young children to help them to actually blow air through the nozzle first etc. The training and support element, whilst evidence-based and making use of secondary care expertise, is actually very simple, and encapsulated in a brief written protocol and manual which could be readily implemented by a nurse during a single consultation.

3.5 Protection against other sources of bias

The recruitment rate and practice demographics of responders/non-responders plus study refusals and documented reasons for these will be examined to evaluate the sample characteristics compared with a more general population. However we anticipate that recruitment will be high because all children will be offered an interesting potential new treatment and improved monitoring in addition to standard care. Careful attention to follow-up of all study patients at 1 and 3 months together with communication of goals will ensure minimal loss to follow up. Notes will be used for 6 months relevant costs e.g. referral.

Measurement bias will be minimised because trial outcomes used have already been assessed for validity in several large trials from our group GNOME, ¹⁵ a pragmatic trial of AOM, ³⁶ and in collaboration with the MRC ^{2,15} We are assessing repeatability, construct, and criterion validity during the pilot phase of the OM questionnaire and also in another cross sectional survey to assess a new web test version of the two alternative 36 item forced choice auditory disability test -the TADAST. ³⁸ The prototype test with restricted research access website www.tadast.soton.ac.uk has been installed Sep 2009. It has on line instructions for self completion, with an initial practise test section.

The autoinflation technique which in this instance is the "balloon blowing" method is easier and more reliable once children have reached the school age group and fun to do, which should minimise performance bias. Company website materials have also been developed to improve patient adherence and standardise the technique. The pilot will seek views from patients, nurses and GPs, to modify procedures and information, and maximise adherence to trial procedures, and should further help minimise performance bias. Both companies involved (Kestrel Medical – Otovent, and Starkey Laboratories - MTP10) have agreed to help with providing trial approved patient information and local research training days. We will ensure that all trial research nurses are trained in accordance with ICH-GCP guidelines and the necessary trial methods and techniques – see also main outcome section.

The main analysis will be on an intention to treat basis i.e. as randomised, to reduce attrition bias and improve generalisability of the sample. We will seek to minimise any loss to follow up in all groups. A per protocol secondary analysis to estimate effects due to compliance will also be performed. Because autoinflation is also available over the counter, possible contamination bias may occur due to use in the control arm, but will be explicitly dealt with by asking patients guardians prior to randomisation to agree not to buy and use autoinflation devices for 3 months if randomised to the control arm. This effect should also be minimised by ensuring good patient/guardian and practice communication and education. Furthermore all patients may receive autoinflation by the end of 3 months as part of the trial if they so choose. At 3 months the guardians will be asked if Otovent was purchased independently to the study, or indeed if any other autoinflation device was used or tried. We will also remind patients and their families that currently Otovent is only recommended in children after they have first seen their own GP, and should be obtained on an FP10 prescription not obtained over the counter. We will ask research nurses to double-check if any "additional" Otovent was inadvertently prescribed in controls during the first 3 month period.

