Autoinflation is a self administered method that aims to insufflate the Eustachian tubes with air, improves tubal ventilation and corrects the negative middle ear pressures often observed in children with glue ear - thus leading to recovery. Autoinflation has probably been done in some form from antiquity most likely as the Valsalva manoeuvre. This is done by trying to do a forced exhalation by contracting the diaphragm and abdominal muscles when the mouth is closed and the nose pinched to try and make the ears "pop" as done by divers or on aeroplanes to equalise the pressure in the ear with atmospheric pressure. Not all children can do this and the most promising way for children to autoinflate effectively is probably by blowing up a balloon through the nostril. This must be done regularly (e.g. x2 or x3 times each day) according to trial evidence, with careful and appropriate training of guardians and children required.

The proposed study technique involves blowing out through each nostril in turn into a purpose fitted connector device (nasal tip or nozzle) with a balloon attached. The pressure generated to inflate the balloon is equivalent to about 30 inches of water pressure, and aids passive opening of the Eustachian tubes (the critical opening pressure required to introduce air into the middle ear reduces as the dimensions of the Eustachian orifice increases with the child's age, so the technique is likely to be more effective in older children as well as easier to do). The introduction of air into the middle ear has been shown to improve or normalise negative middle ear pressure in children performing the technique.²³

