wish (for trial follow -up period 3-6 months). This as previously stated, should improve recruitment rates into the study, which have been refined by the pilot, and should furthermore encourage the active monitoring process for control children up to 3 months including those where there is no initial resolution at 1 month. Parents from each arm will be asked to complete the OMQ-14 functional health status questionnaire that bests predicts QoL (to assess baseline severity in a standardised manner), and also complete a short studyspecific questionnaire. The participants will also be given a weekly symptom diary to complete (for 1 month at the first visit, and 2 months at the second visit). Symptom diaries are based on measures developed in the GNOME study and a previous Acute Otitis Media study. 15,36 Parents will also receive a daily check sheet to complete with their child to assess compliance, record ease of use and provide details of what treatment, if any they have used (see also outcomes section). NRES has suggested giving tokens for children as a reward e.g. Waterstones/HMV tokens, which both groups will receive at 1 and 3 months for returned completed diaries (£7.50 each, total £15), and should also help somewhat to offset travel etc. for families and so improve compliance. Hearing disability will be evaluated at baseline, and 1 month. Pure tone audiometry is not likely to be valid in the usual primary care setting, and history for hearing loss is only 71% sensitive. 11,15,37 Therefore nurses will instruct on use of a web based test: a forced choice two alternative auditory disability and speech reception test (TADAST), which is less prone to invalidation by back ground noise, is already in a standardised format, and was originally developed in primary care to assess children with glue ear.³⁸ The pilot has shown good test-retest repeatability of this new web version in 4-11 year old children (medical student project 2010).

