3.8 Withdrawals

In accordance with recommended ethics practice guardians and children will be free to withdraw from the study at any time without affecting their usual high standard of medical care. Children in the autoinflation group will be advised to stop the intervention in the instance of any suspected related (expected or unexpected) serious adverse events. All children that do cease the intervention will be followed up (unless the parents withdraw consent) as this study an intention to treat analysis.

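### The per-protocol analysis meant to estimate the effect of compliance selects children in one arm only; a pre-specified complier-average causal effect (CACE) analysis answers that question better

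*Protocol*

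**What the plan says.** Section 3.5 sets the main analysis: "The main analysis will be on an intention to treat basis i.e. as randomised, to reduce attrition bias". It then fixes both a second method and its purpose: "A per protocol secondary analysis to estimate effects due to compliance will also be performed". The protocol does not define the per-protocol set, a compliance threshold or the comparator, and it names no instrumental-variable or CACE analysis.

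Most of what a CACE analysis needs is already planned:

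- Section 3.2.3: "Parents will also receive a daily check sheet to complete with their child to assess compliance". The sheet also records any treatment used.
- Section 3.4, on the further packs offered after 1 month: "Uptake will be recorded for concordance/compliance considerations".
- Section 3.5, on control families: "At 3 months the guardians will be asked if Otovent was purchased independently to the study". Nurses also check for prescribing to controls.
- Section 3.8: children who stop the device are still followed up unless consent is withdrawn.

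Two further statements bear on the point. Section 2.3 says of the child's age: "so the technique is likely to be more effective in older children as well as easier to do". Section 1.3 says that in the intervention arm "children with normal tympanometry in both ears at 1 month will discontinue autoinflation", while those with persisting effusion are encouraged to continue.

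**The concern.** Controls are asked not to use a device for 3 months, so nobody can tell which of them would have complied. A per-protocol set can remove poor compliers from the intervention arm but cannot remove their counterparts from the control arm. Dropping controls who obtained a device does not help, because that selects on a different behaviour. Defining the set more closely in an SAP would not restore the randomised comparison either.

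The resulting estimate mixes the effect of the device with any difference in prognosis between children who comply and children who do not. That matters because section 2.2 names compliance as perhaps the main weakness of the technique, and sections 2.2 and 2.3 already lean on results in compliant groups from earlier trials. A per-protocol figure from this trial could be read in the same way.

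**Working it through.** **Inputs from the protocol (section 8.1).** Control cure at 1 month p0 = 45%; odds ratio 2.4; 125 evaluable children per arm; 90% power; 5% alpha, taken as two-sided; 15% loss to follow-up.

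**The plan's own figure.** The intervention cure rate is 2.4×0.45/(0.55+2.4×0.45) = 1.08/1.63 = 66.3%, a difference of 21.3 points. The usual two-proportion formula gives 113 per arm without continuity correction and 122 with it. The latter totals 244, within 3% of the stated 250. 250/0.85 = 294.1, which rounds up to the stated 295. The protocol gives no figure for the per-protocol analysis.

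**Assumed, not in the protocol.** Compliance c of 60–90%; untreated cure gap g of 0–20 points between would-be compliers and non-compliers; no device use in controls; no effect in non-compliers.

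**Derivation.** Randomisation gives both arms the same share c of would-be compliers. Let pc and pn be the untreated cure rates in would-be compliers and non-compliers.

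- p0 = c×pc + (1−c)×pn and g = pc − pn, so pc = p0 + (1−c)×g.
- With a true effect D in compliers, per protocol gives pc + D − p0 = D + (1−c)×g.
- Intention to treat gives c×D.
- CACE is the intention-to-treat difference divided by c, which is D.

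The per-protocol bias is therefore (1−c)×g, in percentage points:

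| c | g = 0 | g = 10 | g = 20 |
|---|---|---|---|
| 90% | 0 | 1 | 2 |
| 80% | 0 | 2 | 4 |
| 70% | 0 | 3 | 6 |
| 60% | 0 | 4 | 8 |

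A negative g reverses the sign.

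**No true effect.** At c = 70% compliers would cure at 48% (g = 10) or 51% (g = 20) against 45%, spurious odds ratios of 1.13 and 1.27. At c = 60% the odds ratios are 1.17 and 1.38. With 125c compliers against 125 controls and a normal approximation, a nominal 5% test rejects in 7.2% of trials (c = 70%, g = 10), 13.9% (c = 70%, g = 20) or 19.6% (c = 60%, g = 20).

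**True complier effect of 21.3 points, c = 70%, g = 20.** Intention to treat: 0.7×21.3 = 14.9. Per protocol: 21.3 + 0.3×20 = 27.3. CACE: 14.9/0.7 = 21.3. In 200,000 simulated trials of 125 per arm, per protocol averaged 27.3 (SE 6.6) and CACE 21.2 (SE 8.7).

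**Three months.** Use after 1 month depends on the 1-month result. If compliance means use over the whole period, children who resolve early look like poor compliers. If stopping as told counts as compliance, early resolvers stay compliant automatically while unresolved children have two more months in which to lapse. The two definitions push the estimate in opposite directions.

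**The case against.** The strongest reply is that this is a secondary analysis mentioned in one sentence, that the set may be defined in an SAP not shown here, and that the proposed replacement has faults of its own. Much of that stands.

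- *Comparator.* A reader might infer that all controls are kept. The protocol does not say so, and its checks on control use suggest that some could be dropped. The asymmetry remains either way.
- *Direction.* A reader might infer upward bias from the remark on age in section 2.3. That remark concerns ease of use and treatment effect, not untreated resolution. Families of children with persisting symptoms might comply more, or children who improve early might stop; either would push the estimate down.
- *Safeguards.* Children judged unable to use the device are excluded before randomisation (sections 3.2.4 and 3.7). Age and unilateral or bilateral disease are minimisation variables, adjusted for in the main model (section 8.2). If carried into the compliance analysis, that adjustment reduces the bias but does not remove unmeasured factors such as family motivation.
- *Size.* Both c and g are assumed, and section 3.1.2 reports good compliance in the pilot. At c = 90% and g = 10 the bias is 1 point against a planned effect of about 21.
- *CACE is not free of assumptions.* Six inflations a day make use a matter of degree. Suppose c = 70%, a 21.3-point effect in compliers and half of that below the threshold. Intention to treat is then 0.7×21.3 + 0.3×10.65 = 18.1, and CACE is 18.1/0.7 = 25.9, which is 4.6 points too high. That exceeds the 3-point per-protocol bias at c = 70%, g = 10. Nurse training and phone support in an open trial could also act apart from device use, although an objective tympanometric outcome makes this less likely for the primary endpoint.

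**Conclusion.** The point holds as a cheap improvement to a secondary analysis. The protocol ties a per-protocol analysis to a question about compliance, and no definition of the set can make that comparison a randomised one. The unadjusted bias is 0 if compliance is unrelated to prognosis and up to 8 points over the assumed ranges of c and g. Its direction is unknown and it would be smaller after adjustment. At 3 months, use is also driven by the earlier outcome.

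The documents do not support saying that the estimate will be too high, or that CACE is unbiased whatever the threshold. Nor is the trial's main conclusion at risk: the intention-to-treat analysis and the sample size are untouched.

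**What to change.** Keep intention to treat as the main analysis. For the compliance question, pre-specify a CACE analysis of the 1-month outcome with:

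- randomised arm as the instrument and the minimisation variables as covariates;
- a compliance measure from the daily check sheets, fixed before the data are seen;
- reported device use in controls counted as receipt, so that the divisor is the difference between arms in the proportion receiving treatment;
- a sensitivity analysis with a low threshold or graded use, because use below the threshold may have some effect;
- a statement of the exclusion restriction, noting that the extra nurse training and phone support may strain it.

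Label any per-protocol result exploratory and open to selection bias, above all at 3 months.

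The cost is a little more analysis work and a wider interval (SE about 8.7 against 6.6 points at c = 70%, g = 20). The data are already to be collected. One detail needs care: families are asked about purchase at 3 months, so for a 1-month analysis the check sheets, or a date added to that question, must show whether control use fell in the first month.
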